### **Sample Size**

Since there is no reference in literature to the efficacy of the treatment under study, as this is a pilot trial, it is not possible to establish a sample size that guarantees adequate significance to the results.

Furthermore, the number of eligible patients cannot be determined a priori because, after two weeks of pre-screening, the enrolled patient could conclude the study without producing data for the endpoint analysis. At the facility involved in this clinical study, will therefore be recruited a total of 40 consecutive patients (20 per arm) who are randomized.

The estimated time for enrollment is approximately 18 months.

### **Medical-surgical procedures and study follow up**

Standard treatment, according to the most recent version of the IWGDF guidelines (IWGDF – International Working Group on Diabetic Foot < <https://iwgdfguidelines.org/wp-content/uploads/2019/05/IWGDF-Guidelines-2019.pdf> > ), includes debridement of the lesion, offloading with a device up to the calf, non-

removable (except for contraindications), dressing of the wound with advanced dressings in use at the trial center and at the home care according to SoC, to be renewed biweekly.

For the purposes of the study, in order to standardize the standard treatment as much as possible, all patients, except for contraindications, will adopt the same brace, made irremovable [Optima Diab, Molliter, Civitanova Marche (23-24)]

The treatment with EmoLED, in addition to the standard treatment, will be performed twice a week in correspondence with the dressing change of the lesion by the Home Care Nursing Service, blinded to the doctors of the specialist center, for twenty consecutive weeks, for a total of 40 treatments.

Treatment with the EmoLED device consists of irradiating each area of 5 cm in diameter of the lesion for 2 minutes; if the lesion is wider than 5 cm in diameter, the applications will be repeated to cover the entire area of interest. EmoLED treatment is additional to standard patient therapy.

During the twenty weeks of treatment with the EmoLED device and until healing, treatments with other types of phototherapies (including photodynamic therapies), topical negative pressure therapy, or other therapeutic interventions in addition to standard therapy will not be allowed.

In the event of clinical signs of infection of the wound, in the case of mild, moderate or severe infection according to I.D.S.A. (25), the lesion will be treated with antiseptic medication and, if deemed necessary by the investigator, with systemic anti-infective therapy, identified by medical personnel. The onset of infection will be reported in the appropriate section of the Data Collection Form and eventually reported to the promoter in case of serious infection (Serious Adverse Event).

In case, therefore, the lesion presents signs of infection as described above, the patient will interrupt their presence in the study and will be treated adequately. The patient can continue the study only if there is a remission of the symptoms of infection. The event will be reported in the appropriate section of the Data Collection Form.

The patient will be invited to a scheduled check-up at the referral center to assess the progress of the lesion, once every 30 days, or as needed.

The patient, if the wound healing occurs while being managed at home, will be invited to return for a check-up visit at the referral center within a week, to confirm the healing.

If at the conclusion of the participation of the patient in the clinical investigation, any additional treatments are required to those normally provided for the clinical condition considered in this study, the sponsor will cover the costs incurred for such treatments.

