### **Information related to the clinical investigation**

#### **Study description**

This clinical study will be a prospective, randomized controlled, double-blind single-center study with the aim of evaluating the clinical efficacy and safety of use of a portable, battery-powered light-emitting device that uses LEDs that emit blue light. The clinical study aims to compare the existing standard treatment for grade IC or IIC neuro-ischemic diabetic foot lesions according to the University of Texas Wound Classification in patients with type I or II diabetes, with a protocol that provides for the administration of the treatment with EmoLED for 20 consecutive weeks in addition to conventional therapy.

Enrolled patients have to be managed in Home Care Nursing Service (by nurses of the "Rete Assistenziale Lesioni Cutanee"), after discharge, twice a week, and have to go to the referral outpatient center participating in the trial once a month for follow-up visits, or in case of adverse events.

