#### *Study secondary endpoints*

1. Healing time (in which healing is represented by a lasting and complete re-epithelialization);
2. Reduction of the lesion surface in both arms, during the 20 weeks, measured in absolute terms (square centimeters) and as % of the initial size;
3. Quality of life (QoL), evaluated both with specific questionnaires (EuroQoL-5D) and generic questionnaires (Wound-QoL);
4. Perception of pain measured with a subjective analogue rating scale (VAS);
5. Assessment of the costs related to the two arms in the perspective of the National Health System, NHS (considering only direct health costs) and in the perspective of the Society (considering beyond direct health costs, direct non-health costs and indirect costs);
6. Patient's satisfaction with the EmoLED therapy, assessed by administering specific questionnaires;
7. Appreciation, complexity and usefulness of the EmoLED therapy by the operators assessed through the administration of specific questionnaires;
8. Security of treatment (number of Adverse Events in the two groups);
9. Evaluation of the cost-effectiveness of using EmoLED for the treatment of ulcers.

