### **Measurable parameters**

Following enrollment and signature of the informed consent, during the first visit / treatment, at the reference outpatient center, the salient data and photographic images of the lesion of each patient will be collected in the appropriate data collection form (see Annex).

During the home visits, twice a week (concomitantly with the dressing change and with the treatment with EmoLED for the Treated Group, respectively), photographic images of the lesion of each patient, some clinical data and the perception of pain through VAS scale will be collected. These variables will be measured at each

visit or until healing. During the visits (to be scheduled at least once every 30 days) carried out at the reference center participating in the trial, the clinical data on the Data Collection Form (see Annex), the photographic images of the lesion of each patient, pain perception using the VAS scale and quality of life data will be collected.

Questionnaires relating to the Quality of Life Section will be administered at the first visit and at the last visit. In particular, standard tools such as the generic questionnaire EQ-5D and the specific questionnaire Wound-QoL will be administered, both available and validated in Italian.

The parameters used that will be found for the definition of the result in the study are:

- Re-epithelialization of the lesion / reduction of the lesion area through data collection form and photographic images of the lesions treated with EmoLED and control lesions (Annexes B, C);
- Intensity of pain perceived by the patient through the VAS scale (Annexes B, C);
- presence of infection (Annexes B, C);
- Level of quality of life perceived by the patient through a questionnaire on the quality of life (EuroQoL and Wound-QoL) (Annexes D, E);
- Appreciation of the therapy (patient) through a specific questionnaire to be filled in by the patient (Annex F);
- Satisfaction, complexity and usefulness of using the device (operator) through a specific questionnaire to be filled in by the operator (Annex G);
- Direct and indirect costs (Annexes H, I);
- Detection of Adverse Events (Annexes B, C).

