#### **Known or predictable factors that may compromise the results and their interpretation**

An incorrect recording of photographic images does not make it possible to determine the area of the lesion via software. This problem is tackled by providing precise instructions on the correct use of the tools available for the retrieval of images.

Discontinuity of patients regarding adherence to plantar offloading can affect recovery times. Before recruiting a patient, the doctor ensures that the patient is available to follow the prescribed therapy and to go to the clinic when required.

In case the patient misses a check-up visit, this can be regained within two days following the scheduled date. If this is not possible, the visit will not be carried out and the patient will be evaluated at the next visit. If the patient misses more than one visit, they will be excluded from the study (drop out).

Other reasons why patients will have to leave the study early are the lack of treatment, with EmoLED or with standard therapy, for more than four consecutive times, or for the lack of a quarter of home visits in total (unless non-treatment is provided for in this Protocol, such as in the case of suspension due to infection). Patients in which it is not possible to establish the exact date of recovery for various reasons, and patients who, in the opinion of the investigator, show a poor compliance with the therapeutic standards required by the study protocol, will also be excluded.

In such cases, the investigator will exclude patients from the study, recording on the data collection form, in addition to the date of exclusion, also the reasons why the patient was excluded.

The patient may, however, withdraw from the study at any time without having to give any explanation to the investigator (withdrawal of consent).

Following the exclusion or abandonment of the study by the patient, the data collection form is identified, scanned and stored.

If a patient withdraws from the study, the Principal Investigator records the event in the identification register and on the data collection form and stores it all.

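### The infection rule pauses the patient's presence in the study, not just treatment, so endpoint measurement may stop after a prognostic post-randomisation event

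*Protocol*

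**What the plan says.** The Protocol section on medical-surgical procedures and follow-up sets the trigger widely: "in the case of mild, moderate or severe infection according to I.D.S.A". It then states that "the patient will interrupt their presence in the study and will be treated adequately" and that "The patient can continue the study only if there is a remission of the symptoms of infection". What is interrupted is presence in the study, not the EmoLED or simulated application.

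The section on known or predictable factors describes the same event more narrowly. Patients leave the study after too many missed treatments or home visits, "unless non-treatment is provided for in this Protocol, such as in the case of suspension due to infection". A separate sentence there drops any patient who misses more than one check-up visit, and it carries no infection exception.

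Under Management of missing data, non-completers stay in the analysis by intention to treat and their missing values are filled by last observation carried forward (LOCF). Gaps in patients who stay in are filled from the neighbouring visits or by LOCF.

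**The concern.** The two sections give site staff different instructions for the same patient. Under one, treatment pauses and measurement goes on. Under the other, the patient is out of the study until the infection clears, and stays out if it does not.

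Infection arises after randomisation and is prognostic for healing. If measurement stops there, a wound that deteriorates keeps its better earlier value, and a wound that would have recovered is frozen at a worse one. If the arms differ in unremitting infections, the comparison is distorted, and the direction depends on what the unmeasured wounds did. An analysis plan cannot recover a measurement that was never taken, so this has to be settled in the conduct rules.

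The main exposure is secondary: "Reduction of the lesion surface in both arms, during the 20 weeks", pain, and possibly quality of life. The Statistics section presents the trial as a proof of concept whose results may inform later sample sizes, so distorted estimates could be carried forward.

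**Working it through.** **1. The provisions side by side**

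| Question | Procedures and follow-up | Known or predictable factors |
|---|---|---|
| What stops? | Presence in the study | Treatment |
| Until when? | Remission | Not stated |
| Does it count towards exclusion? | Not stated | Excused for missed treatments and home visits; no exception for missed check-ups |

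The excused limits are more than four consecutive treatments (5 treatments / 2 per week = 2.5 weeks) and a quarter of home visits (40 / 4 = 10 over the treatment period, about 5 weeks). An interruption spanning two 30-day check-ups could trigger drop-out, but only if visits not held because of the interruption count as missed. The protocol does not settle that.

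**2. Which value would be carried forward**

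- Area and pain: the last value before or at infection.
- Quality of life: the baseline value, if questionnaires are given only at the first and last visits, as several sections say. Measurable parameters also says of the centre visits that "pain perception using the VAS scale and quality of life data will be collected", so a later value may exist.
- Primary endpoint: it changes only for a patient who would have healed by week 24.

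**3. Patients affected** (assumed: 10-30% infected, half not remitting)

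- Low: 40 x 0.10 x 0.5 = 2 (5%).
- High: 40 x 0.30 x 0.5 = 6 (15%).

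**4. Carried area reduction** (assumed log-linear closure at 0.08 per week): 1 - exp(-0.08 x t)

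- t = 4: 27.4%
- t = 8: 47.3%
- t = 12: 61.7%
- t = 20: 79.8%, the value had healing continued; 0% if the wound returned to its initial size.

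**5. Simulation** (10,000 runs, 20 per arm, weekly log slope with mean 0.08 and SD 0.08, no treatment effect on closure, lost patients keep their value from week 4, 8 or 12, area reduction at week 20, two-sided Mann-Whitney test at 0.05; Monte Carlo SE about 0.2 percentage points for the rejection rates)

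| Lost, arm A v arm B | Rejection rate if lost wounds keep healing |
|---|---|
| 0% v 0% | 5.1% |
| 5% v 5% | 5.2% |
| 15% v 15% | 4.8% |
| 5% v 15% | 5.5% |

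At 5% v 15%, the mean difference in median area reduction (A minus B) is:

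| Unmeasured course of lost wounds | Recorded | True |
|---|---|---|
| Healing continues | 4.0 points | 0.1 points |
| Return to initial size | 3.6 points | 8.5 points |

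In the first row the arm with more losses looks worse than it is, by 4.0 - 0.1 = 3.9 points. In the second it looks better than it is, by 8.5 - 3.6 = 4.9 points. Repeat runs of the second scenario gave 3.6 to 4.2 recorded against 8.3 to 9.5 true. With equal loss the mean recorded difference is about 0. At 5% v 10%, with healing continuing, it is 2.0 points.

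**The case against.** The strongest reply is that the protocol largely explains itself. Its own later label for the event is a suspension of treatment, and the wording of the infection rule describes a pause rather than withdrawal. Other sections point towards continued observation. Patients attend the centre "once a month for follow-up visits, or in case of adverse events". Check-ups every 30 days are listed without an infection exception. Infection is itself a recorded parameter with a checkbox at each visit, and remission can be established only by examining the wound. Home visits are twice weekly, so the last value would usually be recent when infection starts.

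This shows that the sections can be reconciled, so it is an ambiguity and not a flat contradiction. It does not remove the problem. None of these provisions requires scheduled measurement during the interruption or a week-24 assessment without remission, and the one explicit rule for this situation points the other way. A recent value at onset also says nothing about the weeks that follow.

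A second reply is that LOCF causes the harm and would affect any drop-out. That is true of the mechanism, but this rule creates avoidable missing data for a reason related to outcome.

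The third reply is about size, and most of it stands. An ulcer with an infection that never remits will rarely be healed at week 24, so the primary endpoint is little affected. Every rate is assumed. The 4-5 point bias needs a threefold imbalance (1 v 3 patients of 20), and the SD of the difference in medians is about 14 points even with no loss. This limits the importance of the point, but it is no reason to leave a cheaply corrected rule as it is.

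**Conclusion.** The concern holds. Followed literally, the infection rule stops endpoint observation after a prognostic post-randomisation event, and it disagrees in scope with the protocol's later description of the same event. The consequence is possible distortion of estimates, chiefly for area, pain and possibly quality of life. It is not inflation of false positives, and the effect on the primary endpoint is small.

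The size cannot be established from the protocol. Under the assumed infection, remission and closure rates, 5-15% of patients are affected, and the bias in median area reduction is about 4 to 5 points at 5% v 15% loss and about zero at equal loss. An infection that remits before week 24 need not cost the primary endpoint. The change should be made because it is cheap; the ambiguity does not invalidate the trial. Confidence is medium, because the harm depends on sites following the literal wording.

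**What to change.** Make three wording changes.

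1. In the procedures and follow-up section, state that infection suspends only the EmoLED or simulated application until remission, in line with the section on known or predictable factors.
2. In the same place, state that the monthly centre visits and the week-24 assessment continue for every randomised patient, whether or not the infection remits.
3. In the section on known or predictable factors, state that check-ups missed because of infection do not count towards drop-out.

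Treatment of the infection is unchanged. The visits are already planned: 24 x 7 / 30 = about 5.6 centre visits per patient. The cost is a few more recorded visits for infected patients. For one infected at week 8 without remission, it is 16 x 7 / 30 = 3.7, or about 4.

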### **Measurable parameters**

Following enrollment and signature of the informed consent, during the first visit / treatment, at the reference outpatient center, the salient data and photographic images of the lesion of each patient will be collected in the appropriate data collection form (see Annex).

During the home visits, twice a week (concomitantly with the dressing change and with the treatment with EmoLED for the Treated Group, respectively), photographic images of the lesion of each patient, some clinical data and the perception of pain through VAS scale will be collected. These variables will be measured at each

visit or until healing. During the visits (to be scheduled at least once every 30 days) carried out at the reference center participating in the trial, the clinical data on the Data Collection Form (see Annex), the photographic images of the lesion of each patient, pain perception using the VAS scale and quality of life data will be collected.

Questionnaires relating to the Quality of Life Section will be administered at the first visit and at the last visit. In particular, standard tools such as the generic questionnaire EQ-5D and the specific questionnaire Wound-QoL will be administered, both available and validated in Italian.

The parameters used that will be found for the definition of the result in the study are:

- Re-epithelialization of the lesion / reduction of the lesion area through data collection form and photographic images of the lesions treated with EmoLED and control lesions (Annexes B, C);
- Intensity of pain perceived by the patient through the VAS scale (Annexes B, C);
- presence of infection (Annexes B, C);
- Level of quality of life perceived by the patient through a questionnaire on the quality of life (EuroQoL and Wound-QoL) (Annexes D, E);
- Appreciation of the therapy (patient) through a specific questionnaire to be filled in by the patient (Annex F);
- Satisfaction, complexity and usefulness of using the device (operator) through a specific questionnaire to be filled in by the operator (Annex G);
- Direct and indirect costs (Annexes H, I);
- Detection of Adverse Events (Annexes B, C).

#### *Registration of clinical data*

The data related to the evaluation of the study endpoints are acquired, for both groups, during the visits.

The parameters of the Data Collection Form, the questionnaires about quality of life and the questionnaire about the acceptability of the therapy are acquired during the outpatient visit at the reference centre and kept on paper for the clinical trial length, and conserved in both paper and digital form; the pictures of the lesion are acquired and kept in digital form, during the length of the clinical trial and afterwards.

The storage coding follows the patient recruitment code and acquisition timing.

During each visit, a picture of the lesion will be taken and analyzed so that the process of healing can be valued in a quantitative and qualitative way.

At each visit, data on the patient's perception of pain will also be collected.

The Quality of Life related questionnaires will be administered at the first visit and at the last visit, scheduled after 24 weeks, at the reference center. In particular, standard tools such as the generic EQ-5D questionnaire, validated in Italian, will be administered. Similarly, the questionnaire for the patient acceptance of the therapy (generic for both the group treated with EmoLED and the control group) will be administered at the

last visit, scheduled after 24 weeks, or on the date of recovery. The operator satisfaction questionnaire (to be administered exclusively to staff belonging to Home Care) will be administered at the end of the study.

*Data collection form (screening period) (Annex A)*

The collection of data relating to the Clinical Section includes the patient's identification code, date of birth, sex and characteristics of the lesion in question. There is also a space for any concomitant pathologies, any drug therapy (to be registered in terms of active substances). The last section is intended for recording the size of the wound.

*Data collection form (Research Center) (Annex B)*

The collection of data relating to the Clinical Section includes the patient identification code, date of birth, sex and characteristics of the lesion to be collected in the initial phase. There is also a space for any concomitant pathologies, any drug therapy (to be registered in terms of active substances), any notes.

The second part of the form is organized as a matrix where the row represents the measurable parameters for each time of observation (reported in column).

At each visit the investigator marks with an "X" the chosen value for each parameter and the most suitable description. The investigator will also fill a check list, for each visit, to ensure that the picture of the lesion has been taken, and there will also be a checkbox in case of presence of infection in the wound bed.

Regarding the measurement of the size of the lesions, with "length" and "width" it is meant the longest diameter of the lesion and the largest diameter orthogonal to the first.

There is also a section dedicated to recording any additional visits, the date of recovery and the observation period following the end of the treatment. On the last page there is a table for reporting adverse events that will occur during the trial. In this table must be reported all types of adverse events (even serious). In this table will be reported the date of onset of the event, the type of event (there are already some entries of common adverse events that may occur on the wound or in the perilesional tissue), the solution implemented (additional therapy, hospitalization, etc.), the date of resolution of the event, the way of resolution and correlation of the event with topical therapy or treatment with EmoLED. The onset of any adverse event (even not serious or unrelated) must be reported to the sponsor, as well as included in the table above. In case of suspected or established correlation of the adverse event with treatment with EmoLED, the event will be declared as an "incident" and the principal investigator will be obliged to report it to the competent authorities as described in paragraph "Incidents and their reporting".

*Data collection form (Home Care) (Annex C)*

During the home visit phase by the home care staff, a short data collection form will be filled out (twice a week) where in addition to the patient's identification code and belonging to the Treated or Control group, the same parameters of the data collection form will be annotated weekly for the Experimental Center. On the last page there is a table for reporting adverse events (see Annex B).

*Data collection form on Quality of Life (Annexes D, E)*

At the first visit and at the last visit to the experimental center, the enrolled patient will be given a form for the collection of data on quality of life, in which the subject is asked to answer some questions (about autonomy, pain, daily discomfort, etc.) also related to the presence of the chronic lesion under examination.

Questionnaires relating to the Quality of Life Section will be administered at the first visit and at the last visit, planned after 24 weeks. In particular, standard tools such as the generic questionnaire EQ-5D and the specific questionnaire Wound-QoL will be administered, both available and validated in Italian.

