#### **Endpoints**

##### *Study primary endpoint*

The primary endpoint of the study will be the percentage of lesions considered healed (meaning as having a lasting and complete re-epithelialization) in the two groups at the twenty-fourth week of observation.

Healing must be confirmed by the Principal Investigator or their staff during an outpatient visit at the reference center participating in the study; the date of the recovery will in any case be indicated as the one of the first response, if it had occurred before the last visit to the reference center.

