#### **Study design**

The study is a double-blind pilot trial on outpatient patients, followed in an integrated way at a specialized center for the care of diabetic foot and Home Care as territorial home nursing service, articulated over a total period of 24 weeks (20 weeks of treatment plus 4 weeks of observation). Therefore, after an initial characterization and treatment setting by the specialist center, the patients will be followed biweekly by the nurses of Home Care, to then be re-evaluated at the center on a monthly basis.

The assessment of the evolution of the lesions will be made at the specialist center, in which the evaluating physician will not be aware of the type of home treatment performed by the patient and its allocation group and the execution of treatment with EmoLED will be performed ensuring the blindness also to the patient. This also ensures an adequate level of masking to ensure that the study is double-blind.

Both for the treatment group and for the control group, the patient will not be aware of the group to which he has been assigned; the operator will make the patient wear glasses (distributed to each patient at the beginning of the study) totally obscuring and will take out of the room any family members or other people before performing/simulating the treatment with the EmoLED device. In case the patient has been assigned to the control group, the operator will simulate to perform the treatment, turning on the device but pointing the light beam away from the patient (e.g. illuminating the floor).

Once the inclusion criteria are verified and the patient has given their consent to participate in the study, a two-week pre-enrollment period will be observed, in which the patient will receive standard treatment (as

indicated below); at the end of the two weeks of pre-enrollment, the patient will be re-evaluated to see if the lesion has not reduced by 50% with standard treatment alone.

If so, the patient will leave the study while, if the lesion has not reached this percentage of re-epithelialization, the patient will be randomized into the two study groups: the control group will continue with only the standard treatment as described above, while the treatment will receive in EmoLED treatment in addition to the standard treatment.

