Patients will be randomized into the two arms of the study according to a list of random numbers generated by special IT tools and communicated by the scientific supervisor to the Care Provider via e-mail.

It is a 1: 1, single-block randomization of 40 patients distributed in the two groups (treated and control). After the two-week enrollment observation period, the Investigator at the outpatient center will ascertains the conditions for the study prosecution and he will notify the Head of the Care Providers to take charge of the patient included in the study and to proceed with the assignment to one of the groups. In this way, the Investigator at the outpatient center will be blinded to the treatment performed at home by the patient.

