#### **Number of experimental medical devices expected to be used**

Each investigator centre involved in the treatment will be provided with 5 EmoLED medical devices, distributed between the Diabetic Clinic and the Home Care.

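### Blinding of the centre assessor who confirms healing is promised but not protected: the Home Care form carries the arm, and no rule keeps it from that assessor

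*Protocol*

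**What the plan says.** **The promise.** Under Study primary endpoint, "Healing must be confirmed by the Principal Investigator or their staff during an outpatient visit at the reference center participating in the study". Under Study design, "the evaluating physician will not be aware of the type of home treatment performed by the patient and its allocation group", and assignment goes through the Head of the Care Providers: "In this way, the Investigator at the outpatient center will be blinded to the treatment performed at home by the patient". The section on medical-surgical procedures repeats that EmoLED is given by Home Care and concealed from the centre's doctors.

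**The record flow.**
- Registration of clinical data: Home Care staff complete Annex C twice a week, and it holds the group, "in addition to the patient's identification code and belonging to the Treated or Control group".
- Measurable parameters: Annexes B and C are both listed as sources for re-epithelialization and lesion area, pain, infection and adverse events.
- Known or predictable factors: patients leave the study if they miss more than four treatments in a row (EmoLED or standard) or a quarter of home visits. "In such cases, the investigator will exclude patients from the study, recording on the data collection form".
- Study primary endpoint, with the procedures section: recovery is dated at the first response. If the wound closes at home, a centre visit follows within a week to confirm it.
- Registration of clinical data: the adverse event table asks whether each event is related to topical therapy or to EmoLED, and the principal investigator must report suspected EmoLED-related events to the authorities.

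**The concern.** The blinding of the primary endpoint rests on one separation: Home Care knows the arm and the centre does not. The healing call is a yes/no judgement by the centre, so its credibility depends on that separation holding in practice.

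Several centre tasks need information that arises at home, and the only home record that the protocol describes carries the arm. A site could meet those needs in the obvious way, by passing Annex C across, and find no form-handling rule telling it not to. The person who confirms healing could then know the arm when making the call. The same person may also exclude a patient for poor compliance as a matter of opinion.

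**Working it through.** The protocol gives no figure on this point and makes no sample size calculation, so there is nothing to reproduce. The check sets the sections side by side and then sizes one call.

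**Step 1. What each centre task needs, and where it is recorded**

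| Centre task | Section | Information needed | Where it arises |
|---|---|---|---|
| Confirm healing | Study primary endpoint | Centre examination | Centre (Annex B) |
| Date recovery at first response | Study primary endpoint; procedures section | Date closure first seen | Possibly Home Care |
| Exclude for missed treatments or home visits | Known or predictable factors | Count of missed sessions and visits | Home Care |
| Relate adverse events to EmoLED; report | Registration of clinical data | Whether EmoLED was given | Home Care |

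Only the first task can be done wholly from the centre's own form. The items listed for Annex B include no group field. The second and third need home data but not the arm: controls also have twice-weekly dressing visits with a simulated session, so a count of misses is the same kind of number in both arms. The fourth may need the arm.

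**Step 2. Is there a barrier?** The sections state that the assessor is blind and route the assignment around the investigator. None says that Annex C is withheld from whoever confirms healing, that an arm-free extract is sent instead, or that arm-dependent tasks go to someone else.

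**Step 3. Size of one swayed call.** Input: 20 per arm (Sample Size). One call changes that arm's healed proportion by 1/20 = 0.05, or 5 percentage points. Two calls in one arm: 2/20 = 10 points.

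**Step 4. Illustration against the 0.05 threshold.** The counts are assumed. Each table below has an observed count under 5, so Fisher's test applies if the protocol's rule means observed counts.
- 11/20 against 4/20: p = 0.0484. One call fewer, 10/20 against 4/20: p = 0.0958.
- 17/20 against 10/20: p = 0.0407. One call fewer, 16/20 against 10/20: p = 0.0958.

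**Step 5. Illustration of bias.** Assume no true effect, Fisher's test throughout, and an assessor who calls a fraction m of unhealed treated lesions healed. The apparent treated rate is then pt = pc + (1 − pc) × m; for pc = 0.30 and m = 0.20, pt = 0.30 + 0.70 × 0.20 = 0.44. Summing exact binomial probabilities over all tables with p < 0.05 favouring EmoLED gives:

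| Assumed healing rate pc | m = 0 | m = 10% | m = 20% | m = 30% |
|---|---|---|---|---|
| 30% | 1.2% | 3.8% | 9.0% | 17.8% |
| 40% | 1.2% | 2.8% | 6.0% | 11.7% |
| 50% | 1.0% | 2.3% | 4.7% | 9.1% |

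These show sensitivity only. The protocol gives no basis for m or pc, and the figures do not cover the chi-square test that it uses for tables without small counts.

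**Step 6. Exclusions are different.** Management of missing data keeps non-completers in the analysis by intention to treat, with the last observation carried forward. An excluded patient stays in the denominator, and the result changes only if that patient's healing status would have changed later. The 5-point figure does not carry over to exclusions.

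**The case against.** The strongest reply is that the protocol states assessor blinding three times and gives a route for assignment that bypasses the investigator. Annex C belongs to Home Care and is completed by its staff, while the recovery date has a place on Annex B. No sentence sends Annex C to the evaluating physician; the phrase about weekly annotation for the centre can mean simply the same parameters as on the centre's form. Missed sessions and a first-closure date can be passed on without the arm. A site that handed Annex C to the assessor would breach the blinding rules, not follow them.

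Most of this stands, and it rules out several stronger readings that a reader might infer:
- *The investigator is required to use Annex C.* The text does not say so; the need for home data is inferred from the tasks above.
- *EmoLED is first given at the centre.* The words "during the first visit / treatment, at the reference outpatient center" follow enrolment and consent. Study design puts two weeks of standard care between consent and randomization, so they can refer to standard care before any arm exists.
- *Devices at the clinic reveal the arm.* The protocol provides "5 EmoLED medical devices, distributed between the Diabetic Clinic and the Home Care". Both arms need a device, because the control simulation switches one on, and its presence at the clinic identifies nobody's group. The wording does sit awkwardly with sections that place the trial treatment in Home Care, and should be reconciled with them.

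The reply does not supply the missing barrier. A statement that someone is blind does not settle how an arm-bearing source form is kept from that person while their tasks draw on home records.

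**Conclusion.** The point holds as a risk to the blinding of the primary endpoint, created by the protocol's own form content and division of tasks. It does not support a conclusion that blinding fails as written, since the protocol states the blinding and conceals the assignment route. Each healing call swayed by knowledge of the arm is worth 5 percentage points in that arm; how many calls would be swayed, if any, cannot be estimated from the document. The conclusion assumes that the annexes, which were not available to check, follow the text's description and carry no handling instruction of their own. It is a cheap and worthwhile improvement: the study is a 40-patient proof of concept, and its results may be used to size later trials, which would inherit any assessor bias.

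**What to change.** 1. Remove the Treated/Control field from Annex C. Keep the arm only in an allocation log held by the Head of the Care Providers.
2. Record each session on Annex C as done or missed, without naming active or simulated treatment.
3. Have Home Care send the centre an arm-free summary before its visits: missed visits or sessions, date closure was first seen, and adverse events.
4. State that any adherence check or attribution to EmoLED that needs the arm is done by already unblinded Home Care or sponsor staff who do not assess healing.
5. Reconcile the device distribution statement with Study design and the procedures section, so that it is clear what devices at the clinic are for.

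The cost is one field removed, one log, and a few sentences of protocol text. The small downside is that Home Care must maintain the log and prepare the summary.
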